3.6.1 Procedures for discontinuation of a subject from investigational product

Previous text:

Any subject who discontinues study treatment for reasons other than objective disease progression should have tumour assessments performed as scheduled in the protocol (See Table 1) until objective disease progression is documented or death occurs, unless consent is withdrawn. Study procedures related to PROs, SAEs and anti-cancer treatment must be captured until the subject no longer has RECIST 1.1 assessments (disease progression or permanent withdrawal from the study).

Revised text:

Any subject who discontinues study treatment for reasons other than objective disease progression should have tumour assessments performed as scheduled in the protocol (See Table 1) until objective disease progression is documented or death occurs, unless consent is withdrawn. ~~Study procedures related to PROs, SAEs and anti-cancer treatment must be captured until the subject no longer has RECIST 1.1 assessments (disease progression or permanent withdrawal from the study).~~ **Refer to Section 4.3 for further details.**

Section of protocol affected:

Table 1 Study Plan

Previous text:

Footnote r Following AZD9291 discontinuation, SAEs considered related to study procedures should continue to be collected until disease progression.

Revised text:

Footnote r Following AZD9291 discontinuation, SAEs considered related to study procedures should continue to be collected **as outlined in Table 8.**

Time relative to dose	Screening (baseline)	Cycle 1 Day 1	Cycle 2 Day 1	Cycle 3 Day 1
24 hours (±1 hour)	X			X (D2, pre-dose)

1 Since there is no dosing at Screening, ECG recordings should start at a time that would be consistent with planned dosing times at Cycle 1 Day 1, Cycle 2 Day 1 and Cycle 3 Day 1 (for baseline purposes).

Revised text:

Time relative to dose	Screening (baseline)	Cycle 1 Day 1	Cycle 2 Day 1	Cycle 3 Day 1
Pre-dose (-10 to 0 min) ²	X ¹	X	X	X
1 hour (±5 min)	X	X		X
2 hours (±10 min)	X	X		X
4 hours (±10 min)	X	X		X
6 hours (±10 min)	X	X		X
8 hours (±10 min)	X	X		X
10 hours (±10 min)	X			X
12 hours (±1 hour)	X			X
24 hours (±1 hour)	X			X (D2, pre-dose)

1 Since there is no dosing at Screening, ECG recordings should start at a time that would be consistent with planned dosing times at Cycle 1 Day 1, Cycle 2 Day 1 and Cycle 3 Day 1 (for baseline purposes).

2 **Window of -10 minutes recommended where feasible (but up to -30 minutes permitted if assessments are performed in different locations in hospital)**

Section of protocol affected:

Table 5 PK blood sample schedule

Previous text:

Time relative to dose	Cycle 1 Day 1	Cycle 2 Day 1	Cycle 3 Day 1
Pre-dose (±5 min)	X	X	X
1 hour (±5 min)	X		X
2 hours (±10 min)	X		X
4 hours (±10 min)	X		X
6 hours (±10 min)	X		X
8 hours (±10 min)	X		X
10 hours (±10 min)			X
12 hours (±1 hour)			X
24 hours (±1 hour)			X (D2, pre-dose)

Revised text:

Time relative to dose	Cycle 1 Day 1	Cycle 2 Day 1	Cycle 3 Day 1
Pre-dose (-10 to 0 min) ¹	X	X	X
1 hour (±5 min)	X		X
2 hours (±10 min)	X		X
4 hours (±10 min)	X		X
6 hours (±10 min)	X		X
8 hours (±10 min)	X		X
10 hours (±10 min)			X
12 hours (±1 hour)			X
24 hours (±1 hour)			X (D2, pre-dose)

1 Window of -10 minutes recommended where feasible (but up to -30 minutes permitted if assessments are performed in different locations in hospital)

Section of protocol affected:

6.3.3 Variables

Previous text:

The following variables will be collect for each AE;

- AE (verbatim)
- The date when the AE started and stopped
- Maximum CTCAE grade/changes in CTCAE grade
- Whether the AE is serious or not
- Investigator causality rating against the Investigational Product (yes or no)
- Action taken with regard to investigational product
- Outcome.

Revised text:

The following variables will be collect for each AE;

- AE (verbatim)
- The date when the AE started and stopped

- **Changes in CTCAE grade (for skin reactions and diarrhoea only); maximum CTCAE grade for all other AEs**
- Whether the AE is serious or not
- Investigator causality rating against the Investigational Product (yes or no)
- Action taken with regard to investigational product
- Outcome.

Section of protocol affected:

6.7.2 Diarrhoea

Previous text:

Recommendations for appropriate management of diarrhoea, including dose-adjustments for adverse events of diarrhoea that are of CTCAE grade ≥ 3 or that are clinically significant and/or intolerable and considered by the investigator to be causally related to AZD9291, will be provided to investigators.

Revised text:

Recommendations for appropriate management of diarrhoea, including dose-adjustments for adverse events of diarrhoea that are of CTCAE grade ≥ 3 or that are clinically significant and/or intolerable and considered by the investigator to be causally related to AZD9291, will be provided to investigators. **Changes in CTCAE grade of diarrhoea will be captured in the AE eCRF.**

Section of protocol affected:

7.2 Dose and treatment regimens

Previous text:

AstraZeneca will supply AZD9291 as tablets for oral administration as a single daily dose of 80 mg. Patients (with the exception of patients with insulin dependent diabetes) must fast for ≥ 1 hours prior to taking a dose to ≥ 2 hour post dose. Water is permitted during this fasting period. Patients will be required to fast (water only) for at least 8 hours prior to the collection of a fasting glucose sample as per the study plan (Table 1) and Section 5.2.1.

Revised text:

AstraZeneca will supply AZD9291 as tablets for oral administration as a single daily dose of 80 mg. Patients (with the exception of patients with insulin dependent diabetes) must fast for ≥ 1 hours prior to taking a dose to ≥ 2 hour post dose. Water is permitted during this fasting

period. **All patients (including insulin dependent diabetics)** will be required to fast (water only) for at least 8 hours prior to the collection of a fasting glucose sample as per the study plan (Table 1) and Section 5.2.1.

Section of protocol affected:

8.1 Statistical considerations

Previous text:

The data cut-off for the primary analysis of ORR will take place 3 months after the last subject enrolled, to allow opportunity for all patients to complete two RECIST follow-up assessments. At this time, DoR and safety/tolerability will also be summarised. The primary analysis CSR will report the analysis of ORR supported by duration of response, and safety and tolerability data.

Revised text:

The data cut-off for the primary analysis of ORR will take place 3 months after the last subject enrolled, to allow opportunity for all patients to complete two RECIST follow-up assessments. At this time **all efficacy, QoL, PK** and safety/tolerability will **also** be summarised **as appropriate based on the amount of data at that time**. The primary analysis CSR will report the analysis of ORR supported by **other efficacy, QoL, PK**, and safety and tolerability data.

Section of protocol affected:

8.4 Outcome measures for analyses

Previous text:

Progression Free Survival (PFS)

PFS is defined as the time from enrolment until the date of objective disease progression or death (by any cause in the absence of progression) regardless of whether the patient withdraws from study therapy or receives another anti-cancer therapy prior to progression. Patients who have not progressed or died at the time of analysis will be censored at the time of the latest date of assessment from their last evaluable RECIST assessment.

Revised text:

Progression Free Survival (PFS)

PFS is defined as the time from **date of first dose** until the date of objective disease progression or death (by any cause in the absence of progression) regardless of whether the patient withdraws from study therapy or receives another anti-cancer therapy prior to

progression. Patients who have not progressed or died at the time of analysis will be censored at the time of the latest date of assessment from their last evaluable RECIST assessment.

Section of protocol affected:

8.4 Outcome measures for analyses

Previous text:

Time to symptom deterioration

For each of the symptoms scales/items in QLQ LC13, time to symptom deterioration will be defined as the time from enrolment until the date of first clinically meaningful symptom deterioration (an increase in the score from baseline of ≥ 5) or death (by any cause) in the absence of a clinically meaningful symptom deterioration, regardless of whether the patient withdraws from study therapy or receives another anticancer therapy prior to symptom deterioration. Death will be included as an event only if the death occurs within two visits of the last PRO assessment where the symptom change could be evaluated.

Revised text:

Time to symptom deterioration

For each of the symptoms scales/items in QLQ LC13, time to symptom deterioration will be defined as the time from **first dose** until the date of first clinically meaningful symptom deterioration (an increase in the score from baseline of ≥ 5) or death (by any cause) in the absence of a clinically meaningful symptom deterioration, regardless of whether the patient withdraws from study therapy or receives another anticancer therapy prior to symptom deterioration. Death will be included as an event only if the death occurs within two visits of the last PRO assessment where the symptom change could be evaluated.

Section of protocol affected:

8.4 Outcome measures for analyses

Previous text:

Time from enrolment to second progression (PFS2) (exploratory)

Time from enrolment to second progression (PFS2) is defined as the time from the date of enrolment to the earliest date of the progression event subsequent to that used for the primary variable PFS or death. The date of second progression will be recorded by the Investigator and defined according to local standard clinical practice and may involve any of; objective radiological or symptomatic progression or death. Patients alive and for whom a second disease progression has not been observed should be censored at the last time known to be alive and without a second disease progression, i.e. censored at the last progression assessment date if the patient has not had a second progression or death).

Time to second subsequent anti-cancer therapy or death is defined as the time from the date of enrolment to the earlier of the date of second subsequent anti-cancer therapy start date, or death date. Any patient not known to have had a further second subsequent therapy or death will be censored at the last known time to have not received second subsequent chemotherapy.

Revised text:

Time from first dose to second progression (PFS2) (exploratory)

Time from **first dose** to second progression (PFS2) is defined as the time from the date of **first dose** to the earliest date of the progression event subsequent to that used for the primary variable PFS or death. The date of second progression will be recorded by the Investigator and defined according to local standard clinical practice and may involve any of; objective radiological or symptomatic progression or death. Patients alive and for whom a second disease progression has not been observed should be censored at the last time known to be alive and without a second disease progression, i.e. censored at the last progression assessment date if the patient has not had a second progression or death).

Time to second subsequent anti-cancer therapy or death is defined as the time from the date of **first dose** to the earlier of the date of second subsequent anti-cancer therapy start date, or death date. Any patient not known to have had a further second subsequent therapy or death will be censored at the last known time to have not received second subsequent chemotherapy.

Section of protocol affected:

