The primary objective of this study is ORR. This is an appropriate primary efficacy endpoint in this NSCLC population and will provide evidence of tumour shrinkage that may be associated with an improvement in PFS, symptom control, and quality of life. Secondary efficacy endpoints are those that are appropriate to this patient population and include PFS, DoR, Disease Control Rate [(DCR): CR + PR + SD] and overall survival. Characterisation of PK as well as the safety and tolerability of AZD9291 will also be assessed as a secondary endpoint.

Several exploratory endpoints will be evaluated (see Section 2.3). These include assessment of the effect of AZD9291 on health state utility (using EQ-5D-5L health state utility index) and resource utilization (e.g. hospital visits). Additional exploratory endpoints will include patient self-reporting of adverse events, further characterisation AZD9291 effects on survival (i.e. impact of baseline potentially prognostic factors on survival, assessment of the course of the disease [post-progression treatment and time from study baseline to progression on post AZD9291 treatment (PFS2)] and the relationship between PK and selected endpoints, tumour samples and biomarkers (ctDNA for the assessment of biomarkers) and tumour biopsy for companion diagnostic development.

The collection of cerebrospinal fluid (CSF) will enable the investigation of the ability of AZD9291 and its metabolites (AZ5104 and AZ7550) to cross the blood brain barrier. Brain metastases occur in 20-30% of patients with advanced NSCLC, and are associated with poor prognosis (Porta 2011). The first generation EGFR TKI agents have demonstrated only limited efficacy in treating brain metastases (Bai 2013, Shimato 2006), however, preclinical data suggests that AZD9291 may be capable of crossing the blood brain barrier (see Investigator Brochure) and potentially may offer better exposures in this anatomically protected location.

Overall, the totality of primary, secondary and exploratory endpoints is AURA2 study will allow a robust characterisation of overall benefit / risk of AZD9291 in a T790M+ advanced NSCLC patient population.

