i To be taken at the same time as the screening biopsy is taken or prior to mutation screening. All plasma samples are required by AstraZeneca, regardless of the outcome of the mutation screening.

j Collect every 6 weeks up to and including progression (corresponding with the RECIST assessments – and continuing after treatment discontinuation in absence of disease progression).

k If for any reason the sample is not drawn prior to first dose it may be taken at any visit until the last study visit.

l To be obtained at one time point at any time from Cycle 2 Day 1 onwards

m At least one lesion, not previously irradiated and not chosen for biopsy during the study screening period, that can be accurately measured.

- n Assess every 6 weeks relative to first dose until end of study (including survival follow-up period) and at the time of progression.
- o Assess every 3 weeks relative to first dose until end of study (including survival follow-up period) and at the time of progression.
- p PRO-CTCAE will only be administered in those countries where a linguistically validated version exists.
- q Assessed at Cycle 7 Day 1 then every 3 weeks relative to first dose thereafter until end of study (including survival follow-up period) and at the time of progression.
- r Following AZD9291 discontinuation, SAEs considered related to study procedures should continue to be collected until disease progression.
- s Survival status including anti-cancer treatment to be performed every 6 weeks (relative to first dose) following disease progression or withdrawal from treatment.
- t Record subsequent response/progression data every 6 weeks until first confirmed disease progression on a subsequent treatment.

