4.3.4 Survival follow-up

Assessments for survival should be made every 6 weeks (relative to first dose) following objective disease progression or withdrawn from treatment. Survival information may be obtained via telephone contact with the patient, patient's family or by contact with the patient's current physician. In addition to the survival status, the following assessments are also required post progression as detailed in the study plan (see [Table 1](#)):

- EORTC QLQ-C30 and EQ-5D-5L every 6 weeks.
- EORTC QLQ LC13 and PRO-CTCAE every 3 weeks.
- Anti-cancer therapy collected every 6 weeks.
- Subsequent response/progression data every 6 weeks until the first confirmed disease progression on a subsequent treatment.

Survival data will be collected up to the time of the final OS analysis. Patients should be contacted in the week following the data cut-off for the final survival analyses to provide complete survival data.

The status of ongoing, withdrawn (from the study) and “lost to follow-up” patients at the time of an overall survival analysis should be obtained by the site personnel by checking the patients notes, hospital records, contacting the patients general practitioner and checking publicly available death registries. In the event that the patient has actively withdrawn consent to the processing of their personal data, the vital status of the patient can be obtained by site personnel from publicly available resources where it is possible to do so under applicable local laws.

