5.1.2 RECIST 1.1 Independent Central Review assessment

The primary analysis for this study will be based on ORR using Independent Central Review (ICR) of patients with measurable disease at baseline as assessed by the ICR, according to RECIST 1.1. All scans from all patients (with both progressive and non-progressive disease by investigator assessment), used in the assessment of tumours using RECIST 1.1 will be conducted. All imaging assessments including unscheduled visit scans will be collected on an ongoing basis and sent to an AstraZeneca appointed CRO to enable central analysis. Results of this independent review will not be communicated to Investigators and the management of patients will be based solely upon the results of the RECIST 1.1 assessment conducted by the Investigator.

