5.8 Post progression outcomes

The date of second progression will be recorded by the Investigator and defined according to local standard clinical practice and may involve any of; objective radiological or symptomatic progression or death. Second progression status will be reviewed every 6 weeks following the progression event used for the primary variable PFS (the first progression) and status recorded. To support PFS2, the time to start of subsequent treatment will be recorded.

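### The PFS2 event does not require a subsequent therapy, so further worsening on AZD9291 can count as second progression, contrary to Section 1.3

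*Supplement*

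**What the plan says.** The protocol describes second progression in five places.

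- **Section 8.4 (Amendment 2).** PFS2 runs from first dose to "the earliest date of the progression event subsequent to that used for the primary variable PFS or death". On who decides, it says: "The date of second progression will be recorded by the Investigator and defined according to local standard clinical practice". Radiological progression, symptomatic progression and death are all accepted.
- **Section 5.8.** "Second progression status will be reviewed every 6 weeks following the progression event used for the primary variable PFS (the first progression"). The next therapy appears only as supporting information: "To support PFS2, the time to start of subsequent treatment will be recorded".
- **Section 1.3.** The exploratory endpoint is described as "time from study baseline to progression on post AZD9291 treatment (PFS2").
- **Section 4.3.4.** Sites collect: "Subsequent response/progression data every 6 weeks until the first confirmed disease progression on a subsequent treatment".
- **Table 1, footnote t.** "Record subsequent response/progression data every 6 weeks until first confirmed disease progression on a subsequent treatment".

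Amendment 2 moved the origin of PFS2 from enrolment to first dose and left the event rule as it was. Neither amendment changes Section 1.3, Section 4.3.4, Section 5.8 or footnote t on this point, so all five statements are current.

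**The concern.** Sections 8.4 and 5.8 define the event by its order: it is the next progression after the PFS event. Sections 1.3 and 4.3.4 and footnote t define it by the treatment on which it occurs. The two agree only if every patient changes therapy between the first and the second progression, and the protocol does not ensure that. Under Sections 1.5 and 4.2 a patient may stay on AZD9291 after RECIST progression.

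A programmer following Section 8.4 and one following Section 1.3 could therefore assign different PFS2 dates to the same patient. There is also a gap between the rule under which sites collect the data and the rule under which the data are to be analysed.

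**Working it through.** The plan gives no figure for PFS2, so there is nothing to reproduce. The check applies the two rules to the patient courses that the protocol allows.

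Notation: P is the progression used for PFS, W a later worsening while still on AZD9291, S the start of the next anticancer therapy, and X the first progression on that therapy. All times run from first dose.

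**Course 1: first progression, stop, next therapy, progression on it (P < S < X).** Both rules give X. There is no conflict.

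**Course 2: treated beyond progression (P < W < S < X).** Section 4.2 keeps these patients on treatment visits without study RECIST assessments, so W would come from local imaging or symptoms, which Section 8.4 accepts.
- Section 8.4 gives W.
- Section 1.3 gives X.
- The shortfall is X − W = (S − W) + (X − S): the remaining time on AZD9291, plus any gap, plus the time from the start of the next therapy to progression on it.
- If the patient dies at D without starting another therapy, Section 8.4 still gives W. The Section 1.3 event, with death included, falls at D.

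In this course the Section 8.4 date is always the earlier one, so PFS2 can only be shortened.

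**Course 3: stops AZD9291 without progression, starts new therapy, progresses at X, progresses again at Y (S < X < Y).** Section 8.4 counts progression for PFS even when another anticancer therapy has been given first, and Section 4.3.3 continues scans in patients who stop without progression. Here X is therefore the PFS event.
- Section 8.4 gives Y.
- Section 1.3 gives X, so one event serves as both PFS and PFS2.
- Footnote t and Section 4.3.4 end collection at X, so Y may never be recorded.

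In this course the mismatch runs in the opposite direction. It is thus not correct that the Section 8.4 date is never later than the Section 1.3 date. Shortening is the direction for patients treated beyond progression.

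**Which first progression?** Section 8.9.2 presents PFS on independent central review (ICR), with investigator assessment as a sensitivity analysis. Section 5.1.2 says of the central review: "Results of this independent review will not be communicated to Investigators". The person who records the second progression therefore does not know the central date of the first. The PFS2 sentence calls PFS the primary variable, but the primary variable in Section 8.9.1 is ORR, so that phrase does not identify an assessor.

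**Size.** Sizing would need the share of patients who worsen on AZD9291 after progression, and X − W in each of them. The documents give neither, nor a rate of disagreement between central and investigator progression.

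**The case against.** The strongest defence is that collection supplies the missing link. In Table 1 the row for subsequent response and progression data refers to Section 5.8, is marked only under survival follow-up, and carries footnote t. The treatment-period columns have no row for second progression. On that reading, worsening on AZD9291 would not clearly be captured as a second progression. This has weight, and it makes course 2 less certain in practice. It does not remove the conflict, because Section 5.8 itself starts the review at the PFS event and Section 8.4 sets no therapy condition.

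A second defence is that Section 8.9.6 defers further PFS2 details to the SAP, which is not shown. Derivation detail can properly sit there. The disagreement about what the event is, however, lies within the protocol.

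Stronger readings are tempting, and the documents do not support them.

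- A reader might infer that PFS2 is anchored to central review, so that an investigator's own first progression, falling after an earlier central one, must count as the second. The PFS2 sentence does not name central review, PFS is planned on both assessments, and no text tells a programmer to relabel the investigator's first progression. For the same reason, a patient without a centrally read progression lacks a reference event only if central review is read into the sentence. What stands is that the anchor is not stated.
- A reader might size the effect with an assumed share of patients and the next-line PFS figures in Section 1.1 (1.7 to 6.2 months on EGFR-TKI re-treatment; 3.3 and 4.4 months in two afatinib trials). No such share is given, and those figures are for patients after earlier EGFR-TKIs, not after AZD9291.
- A reader might take PFS2 as a test of whether benefit carries over to the next line. Section 1.3 speaks only of assessing the course of the disease, and a single-arm study has no comparator for such a claim.

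**Conclusion.** The concern holds as an internal contradiction with a practical consequence. The event rule in Sections 8.4 and 5.8 admits progression on AZD9291 itself, whereas Sections 1.3 and 4.3.4 and footnote t concern progression on later treatment. Where worsening on continued AZD9291 is recorded as second progression, PFS2 ends too early for its stated meaning. The direction in those patients is certain; the amount cannot be derived. The conclusion assumes that some patients continue AZD9291 beyond progression, as the protocol permits, and that their later worsening is recorded.

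The unnamed assessor of the first progression is a secondary gap. The impact is confined to an exploratory, descriptive endpoint: ORR, its precision and the sample size do not depend on it.

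**What to change.** Reword Sections 8.4 and 5.8, and carry the same text into the SAP:

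1. Define PFS2 as time from first dose to the first investigator-recorded progression after the start of the first subsequent anticancer therapy, or death from any cause.
2. State that progression while AZD9291 is still the only therapy is not a PFS2 event.
3. Name investigator-assessed progression as the reference for first progression, and drop the reference to PFS as the primary variable.
4. State the rule for patients who start a new therapy before any progression: either their first progression on it counts for both PFS and PFS2 by intent, or a further progression is required.

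The cost is mainly wording. Subsequent anticancer therapy is already collected every 6 weeks under Sections 4.3.3 and 4.3.4, and the time to its start is recorded under Section 5.8. No visits or scans are added. The one possible exception is item 4: if a further progression is required, the stopping point for collection in Section 4.3.4 and footnote t must be extended for those patients.
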